## **6.9 Prior and Concomitant Therapy**

Any medication or vaccine (including over the counter or prescription medicines, recreational drugs, vitamins, and/or herbal supplements) that the participant (except for screen failures) is receiving at the time of enrollment or receives during the study, or other specific categories of interest such as cholesterol lowering therapy within the last 12 months must be recorded along with:

- Reason for use
- Dates of administration including start and end dates
- Dosage information including dose, frequency and route.

Participants will be required to continue on stable doses of their dyslipidemia maintenance therapy (SoC) throughout the study to minimize the risk of disease worsening during the study.

The Study Clinical Lead should be contacted if there are any questions regarding concomitant or prior therapy.

Concomitant medications that contain a black box warning for significant QT prolongation are prohibited within this study.

Fibrate therapy and derivatives are prohibited.

Paracetamol at doses of £ 2 grams/day, is permitted for use any time during the study. Other concomitant medication may be considered on a case-by-case basis by the investigator in consultation with the Study Clinical Lead if required.

### **6.9.1 Rescue Medicine – Not Applicable**

## 7 DISCONTINUATION OF STUDY INTERVENTION AND PARTICIPANT DISCONTINUATION/WITHDRAWAL

Discontinuation of specific sites or of the study as a whole are handled as part of [Appendix A](#).

It may be necessary for a participant to permanently discontinue study intervention. Note that discontinuation from study intervention is not the same thing as a discontinuation or withdrawal from the study (see Section [7.2](#)).

### 7.1 Discontinuation of Study Intervention

An individual participant will not receive further IMP if any of the following occur in the participant in question:

- Hy's Law (HL) defined as 'an increase in AST of ALT  $\geq 3 \times$  ULN and TBL  $\geq 2 \times$  ULN' where no other reason, other than IMP, can be found to explain the combination of increases.
- A severe hypersensitivity reaction.
- Participant decision. The participant is at any time free to discontinue treatment, without prejudice to further treatment.
- An SAE that is assessed as possibly related to the study intervention by the Investigator.
- An AE or other safety reasons as judged by the investigator and/or sponsor where continued treatment may put the participant at undue risk.
- Severe noncompliance with the CSP.
- Pregnancy; if a participant becomes pregnant during the study the study intervention should be discontinued immediately and a Sponsor representative notified.
- Signs or symptoms of severe hepatic impairment, as described in Section [7.1.1](#).
- Cardiovascular findings, as described in Section [7.1.2](#).
- Respiratory symptoms, as described in Section [7.1.3](#)

If a participant discontinues IMP, he or she will be encouraged to return to the study site for the Early Discontinuation Visit (EDV; see [Table 1](#)). Where possible, the EDV should be at the next visit according to the original visit schedule, unless consent is withdrawn from further study participation, or the participant is lost to follow-up. Participants attending an EDV should also be asked to return for a follow-up visit (Visit 8, as if they have completed all doses) unless they are unable or unwilling to return.

If study intervention is permanently discontinued, the participant should, if at all possible, remain in the study. See the SoA (Section [1.2](#)) for data to be collected at the time of discontinuation of study intervention and follow-up and for any further evaluations that need to be completed.

### **7.1.1 Liver Chemistry Stopping Criteria**

Discontinuation of study intervention for abnormal liver tests is required by the investigator when a participant meets one of the conditions outlined below or in the presence of abnormal liver chemistries not meeting protocol-specified stopping rules, if the investigator believes that it is in best interest of the participant.

- ALT and/or AST are  $> 3 \times \text{ULN}$  and TBL  $> 2 \times \text{ULN}$
- ALT and/or AST are  $\geq 5 \times \text{ULN}$  for  $\geq 14$  consecutive days, at any time after initial confirmatory results
- ALT and/or AST are  $> 8 \times \text{ULN}$
- ALT or AST  $> 3 \times \text{ULN}$  with the appearance of fatigue, nausea, vomiting, right upper quadrant pain or tenderness, fever, rash, and/or eosinophilia ( $>5\%$ )
- ALT or AST  $> 3 \times \text{ULN}$  and INR  $> 1.5$  (applicable for participants with a baseline INR  $\leq 1.1$ )

Please refer to [Appendix E](#) for further instruction on cases of increases in liver biochemistry and evaluation of Hy's Law

### **7.1.2 Cardiac Stopping Criteria**

Discontinuation of study intervention for abnormal cardiac tests is required by the investigator when a participant meets one of the conditions outlined below:

- Average absolute (regardless of baseline value) cardiac QTc interval corrected for heart rate by QTcF  $> 500$  msec, or an increase of QTcF  $> 60$  msec above the baseline value, confirmed (persistent for  $\geq 5$  minutes) on repeat triplicate 12-lead ECGs.

Any one of the following:

- Tachycardia, defined as resting supine pulse rate  $> 125$  beats per minute persisting for at least 10 minutes.
- Symptomatic bradycardia, defined as resting supine pulse rate  $< 40$  beats per minute while awake, persisting for at least 10 minutes.
- Asymptomatic bradycardia, defined as resting supine pulse rate  $< 30$  beats per minute while awake persisting for at least 10 minutes.
- Hypertension, defined as an increase from baseline in resting supine systolic  $> 40$  mmHg or above 180 mmHg and persisting for at least 10 minutes and/or increase from baseline in resting supine diastolic BP  $> 20$  mmHg or above 100 mmHg and persisting for at least 10 minutes.

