Section 5.2 Exclusion criteria 10	Change: Uncontrolled hypertension defined as average sitting DBP > 90 mmHg changed from DBP > 100 mmHg, at Visit 1.	To allow sufficient window between exclusion criteria and stopping criteria.	Substantial
Section 5.2 Exclusion criteria 12	Potassium < LLN added to exclusion criteria	Update based on FDA recommendation	Substantial
Section 5.2 Exclusion criteria 13	Addition of further detail to exclusion criteria	Update based on FDA recommendation	Substantial
Section 5.2 Exclusion criteria 22	Addition of exclusion of fibrate therapy & derivatives	Previously mentioned incorrectly as part of inclusion criteria 5	Substantial
Section 6.1.1, Table 4, Investigational Products	Clarification on tablet shape	Clarification	Non-substantial
Section 6.1.1 Investigational Products	Addition of composition of the placebo.	Update based on FDA recommendation	Non-substantial
Section 6.3 and Section 9.4.1	Clarify randomization for Japan and rest of the world	Add clarity on randomisation set up	Non-substantial
Section 7.1.1 liver chemistry stopping criteria	Addition of criteria	Update based on FDA recommendation	Substantial
Section 7.1.2. cardiac stopping criteria	Addition of clarification that ECGs will be triplicate	Clarification	Non-Substantial
Section 7.1.3 respiratory stopping criteria	Clarification of criteria	Update based on FDA recommendation	Substantial

Section Number and Name	Description of Changes	Brief rationale	Substantial/ Non-substantial
Section 8 Study Assessments and procedures	Added: The approximate amount of blood collected from each participant over the duration of the study is around 300ml (approximately 20 tablespoons)	Add clarity on approximate blood collection	Non-substantial
Section 8.1, Table 5 and Section 9.4.2.2: Statistical Analysis, Efficacy, Secondary Endpoint(s)	Added clarification that the VLDL-C will be calculated from standard lipid profile.	Clarification	Non-substantial
Section 8.2.3 Electrocardiograms	Change: The participant should be in a resting, seated position for at least 10 minutes	Updated duration of resting position to align with cardiac stopping criteria	Substantial
Section 8.4 Pharmacokinetics	Clarification regarding collection of PK samples	Clarification	Non-Substantial
Table 6	Removal of annotation mark corresponding to Leukocyte differential count	Correction due to no corresponding footnote	Non-substantial

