## 1.2      Schedule of Activities

The Schedule of Activities (SoA) is provided in [Table 1](#).

**Table 1** Schedule of Activities

	Screening	Treatment period							Final follow-up/EDV
Visit number	1	2	3	4	5	6	7	8	
Study day	D -21 to D -1	D1	D8	D15	D29	D57	D85	D99	
Visit window			± 3 days						
Informed consent	X								
Inclusion/exclusion criteria	X	X							
Demographic data	X								
Medical history	X								
Height, weight, and BMI (height at screening only)	X	X	X	X	X	X	X	X	
Drugs of abuse screening a	X								
Urine pregnancy test (local) b	X	X							
FSH	X								
LH	X								
HbA1c	X							X	
Serology	X								
COVID-19 test c	X	X							
Concomitant medication review	X	X	X	X	X	X	X	X	
Dispensing of AZD0780/Placebo (35 tablets per bottle)		X			X	X			
Study intervention administration (AZD0780/Placebo)		X (Once daily oral dosing; Day 1 through Day 84)							

**Table 1** Schedule of Activities

	Screening	Treatment period						Final follow-up/EDV
Visit number	1	2	3	4	5	6	7	8
Study day	D -21 to D -1	D1	D8	D15	D29	D57	D85	D99
Visit window			± 3 days					
Safety and Tolerability								
Adverse event review	X (SAEs only)	X (AEs as of dosing)	X	X	X	X	X	X
Physical examination (full)	X	X						X
Physical examination (brief)			X	X	X	X	X	
Vital signs (BP, pulse and temperature, respiratory rate, pulse oximetry) d	X	X	X	X	X	X	X	X
12-lead safety ECG e	X	X	X	X	X	X	X	X
Clinical safety laboratory evaluations (chemistry, hematology, coagulation, urinalysis)	X	X	X	X	X	X	X	X
Urine renal safety biomarkers: albumin, creatinine, total protein	X	X	X	X	X	X	X	X
Efficacy/Pharmacokinetics/Pharmacodynamics (fasted)f								
Lipid profile (TC, HDL-C, non-HDL-C, triglycerides)	X	X	X	X	X	X	X	X
LDL-C	X	X	X	X	X	X	X	X
ApoB		X	X	X	X	X	X	X

**Table 1** Schedule of Activities

	Screening	Treatment period							Final follow-up/EDV
Visit number	1	2	3	4	5	6	7	8	
Study day	D -21 to D -1	D1	D8	D15	D29	D57	D85	D99	
Visit window			± 3 days						
ApoA1		X			X	X	X	X	
Lp(a)		X			X	X	X	X	
hsCRP		X			X	X	X	X	
PK plasma samples f			X	X	X	X	X		
Exploratory									
Blood sample for total PCSK9		X							
Blood (serum) sample for biomarker analyses		X			X	X	X	X	
Blood (plasma) sample for biomarker analyses		X			X	X	X	X	

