### **Medical Conditions**

- 1 Estimated glomerular filtration rate (eGFR) < 45 mL/min/1.73m^2 using the Chronic Kidney Disease-Epidemiology Collaboration (CKD-Epi 2021(Age, Sex)) equation at Visit 1.
- 2 History or presence of gastrointestinal, hepatic or renal disease or any other conditions known to interfere with absorption, distribution, metabolism, or excretion of drugs.
- 3 Any uncontrolled or serious disease, or any medical (eg, known major active infection or major hematological, renal, metabolic, gastrointestinal, respiratory, or endocrine dysfunction) or surgical condition that, in the opinion of the investigator, may either interfere with participation in the clinical study and/or put the participant at significant risk.
- 4 Poorly controlled type 2 diabetes mellitus, defined as HbA1c > 10% at Visit 1.
- 5 Acute ischemic cardiovascular event in the last 12 months prior to randomization however patients can be included if it is > 6 months from coronary artery bypass graft surgery (CABG) surgery and > 3 months after percutaneous coronary intervention (PCI).
- 6 Heart failure with New York Heart Association (NYHA) Class III-IV.
- 7 Malignancy (except non-melanoma skin cancers, cervical in-situ carcinoma, breast ductal carcinoma in-situ, or Stage 1 prostate carcinoma) within the last 10 years.
- 8 Recipient of any major organ transplant, eg, lung, liver, heart, bone marrow, renal.
- 9 LDL or plasma apheresis within 12 months prior to randomization.
- 10 Uncontrolled hypertension defined as average sitting SBP > 160 mmHg or DBP > 90 mmHg at Visit 1. It is recommended that antihypertensive treatment should be considered/initiated at the PI's discretion and in accordance with applicable clinical guidelines in order to optimize blood pressure for participants with hypertension during the clinical study.
- 11 Heart rate after 10 minutes supine rest < 50 bpm or > 100 bpm at Visit 1.
- 12 Any laboratory values with the following deviations at Screening Visit 1; test may be repeated at the discretion of the investigator if abnormal:
  - (a) Any positive result on screening for hepatitis B, hepatitis C or HIV.

- (b) ALT > 1.5 × ULN
- (c) AST > 1.5 × ULN
- (d) TBL > ULN
- (e) Hemoglobin < 12 g/dL in men or < 11 g/dL in women
- (f) Potassium < LLN

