### **8.2.2 Vital Signs**

Vital signs will be performed at timelines as specified in the SoA (Section [1.2](#)). Vital signs will be assessed before any interventional study procedures (blood sampling, ECG, IMP administration). The participant should be in a resting, seated position for at least 5 minutes prior to the collection of vital sign, as follow:

- Body temperature (measured in Celsius). Oral measurement is preferred, but other methods are acceptable as per local standards of care
- Heart (pulse) rate
- Respiratory rate
- Oxygen saturation ( $SpO_2$ ) measured by pulse oximetry
- Blood pressure (systolic and diastolic)

Blood pressure and pulse measurements should be taken by an adequately trained health care professional and assessed with a completely automated device (a calibrated sphygmomanometer is preferred). If not available, another device calibrated carefully in

proportion to a mercury sphygmomanometer should be used. The use of aneroid manometers should be avoided. An appropriate cuff size must be used to ensure accurate measurement. The disappearance of sound (Korotkov Phase V) should be used for the diastolic reading.

Blood pressure and pulse measurements should be assessed with the participant rested in a seated position, their back supported and feet on the ground. Three consecutive blood pressure and pulse readings should be recorded at intervals of at least 2 minutes. The average of the SBP, DBP and pulse readings should be recorded in the eCRF.

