### **8.2.3      Electrocardiograms**

12-lead ECG will be performed at timepoints as specified in the SoA (Section [1.2](#)).

All 12-lead ECGs will be obtained in triplicate with no more than a 5-minute interval between each reading using a properly maintained and calibrated machine. The mean value from the three ECG readings will be recorded in the eCRF. The recordings should be done after the participant has been lying down to rest for at least 10 minutes. For participants with pacemakers, ECG variables should be read manually. ECGs may also be performed according to clinical judgment or as indicated based on any symptoms or clinical events (eg, cardiac arrhythmia).

The following ECG parameters should be collected: PR interval, RR interval, QRS duration, QT and QTcF intervals, and heart rate. An overall evaluation of the ECG results should also be performed.

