4.6.5 Vital Signs

4.6.5.1 Definitions and Derivations

The following vital signs will be measured:

- Body weight (kg)
- Body temperature (degrees Celsius)
- Heart (pulse) rate (bpm)
- Respiratory rate (1/min)
- Oxygen saturation (SpO₂)
- Systolic blood pressure (SBP) (mmHg)
- Diastolic blood pressure (DBP) (mmHg)

Vital signs will be collected at the visits indicated in the SoA (see CSP).

Additionally, vital signs values will be classified as normal (if value is within normal reference range), low (if value is below the normal reference range or limit), and high (if value is above the normal reference range or limit) according to the normal reference values given in [Table 11](#) below. Based on the categories presented in [Table 11](#) variables may have 2-level classification and 3-level classification.

Systolic and diastolic blood pressure will be measured in triplicates and the mean of the three measurements will be collected in the EDC and used in the subsequent analyses.

Table 11 - Vital Signs Normal Reference Ranges

Parameter	Normal reference range
Systolic blood pressure	< 140 mmHg
Diastolic blood pressure	< 90 mmHg
Heart (pulse) rate	50-100 bpm
Body temperature	≤ 37°C
Oxygen saturation	≥ 95%
Respiratory rate	12-20 per minute

Abnormalities in Vital Signs

Treatment emergent abnormalities are defined as abnormalities that manifested after the first administration of study treatment.

The presence of the abnormalities will be determined based on the following criteria (at any time during treatment/study, as applicable):

1. Systolic blood pressure
 - a. Maximum value is > 40 mmHg increase from baseline
 - b. Maximum value is > 180 mmHg
 - c. Maximum value is ≥ 140 mmHg with ≥ 20 mmHg increase from baseline
 - d. Maximum value is ≥ 160 mmHg with ≥ 30 mmHg increase from baseline
 - e. Maximum value is ≥ 180 mmHg with ≥ 40 mmHg increase from baseline
 - f. For change from baseline to mean value
 - i. > 10 mmHg
 - ii. > 20 mmHg
 - iii. > 30 mmHg
 - iv. > 40 mmHg
2. Diastolic blood pressure
 - a. Maximum value is > 20 mmHg increase from baseline
 - b. Maximum value is > 100 mmHg
 - c. Maximum value is ≥ 90 mmHg with ≥ 10 mmHg increase from baseline
 - d. Maximum value is ≥ 100 mmHg with ≥ 20 mmHg increase from baseline
 - e. For change from baseline to mean value
 - i. > 10 mmHg
 - ii. > 20 mmHg
 - iii. > 30 mmHg
 - iv. > 40 mmHg
3. Heart rate

- a. Maximum value is > 100 beats/min with > 20 beats/min increase from baseline

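### The hypertension stopping rule sets change-from-baseline limits in supine blood pressure, but no supine baseline blood pressure is scheduled

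*Protocol*

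**What the plan says.** Protocol 7.1.2 lists conditions under which the investigator must discontinue study drug. The blood pressure condition reads "Hypertension, defined as an increase from baseline in resting supine systolic" pressure of more than 40 mmHg, or a value above 180 mmHg. The diastolic counterpart, also supine, is a rise of more than 20 mmHg or a value above 100 mmHg. Each must persist for at least 10 minutes.

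The measurement instructions use a different posture. Protocol 8.2.2 states: "Blood pressure and pulse measurements should be assessed with the participant rested in a seated position". It asks for three readings at least 2 minutes apart and records their average. Table 1 has a single blood pressure item, in the row that begins "Vital signs (BP, pulse and temperature, respiratory rate, pulse oximetry", and no supine row. Exclusion 10 is also seated: "Uncontrolled hypertension defined as average sitting SBP" above 160 mmHg, or diastolic above 90 mmHg.

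Two planned measurements are taken lying down, and neither includes blood pressure. Exclusion 11 concerns "Heart rate after 10 minutes supine rest" at Visit 1. For the ECG, 8.2.3 says: "The recordings should be done after the participant has been lying down to rest for at least 10 minutes". The ECG variables it lists are intervals and heart rate.

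Protocol 9.4.1 defines baseline as the last non-missing value before the first dose, unless stated otherwise. SAP 3.3.1.2 is similar. Section 7.1.2 states no baseline of its own.

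**The concern.** A limit on change from baseline needs a baseline taken the same way as the later reading. Here the rule names one posture and the schedule supplies the other, and no text says that a seated value may stand in for a supine one. Because the rule is mandatory, its limits should work with the readings that the protocol collects. If a site follows the wording exactly, the participant's postural difference enters the measured change. Depending on its sign, dosing could then stop for a smaller rise than intended, or continue through a larger one.

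**Working it through.** There is no figure in the plan to reproduce. The check sets the rule beside the schedule and then works out what a mixed comparison does.

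**1. Which limits need a baseline (7.1.2).** There are four: systolic rise > 40 mmHg, systolic value > 180 mmHg, diastolic rise > 20 mmHg, diastolic value > 100 mmHg. Two of the four are changes and need a supine baseline. The two absolute limits need only a reading on the day.

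**2. What is scheduled (Table 1, 8.2.2, 8.2.3, exclusions 10 and 11).** Seated blood pressure is scheduled at Visits 1 to 8. The number of scheduled supine blood pressure readings is 0.

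**3. What baseline results.** Applying 9.4.1 or SAP 3.3.1.2 to the planned data gives a seated pre-dose value.

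**4. Effect of each way of applying the rule.** Let B be the seated baseline, r the posture-matched rise, and d the supine-minus-seated difference, assumed constant within a participant (systolic and diastolic d may differ).
- Seated reading, seated baseline: the change is (B + r) - B = r, so the limits are 40 and 20 mmHg.
- Supine reading, supine baseline: the change is (B + d + r) - (B + d) = r, so the limits are 40 and 20 mmHg.
- Supine reading, seated baseline (the literal reading): the change is (B + d + r) - B = r + d. The rule triggers when r > 40 - d (systolic) or r > 20 - d (diastolic).

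The documents give no value for d. The range below is an assumption, for illustration only, and applies only to the third case.

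| Assumed d (mmHg) | Systolic rise needed | Diastolic rise needed |
|---|---|---|
| -10 | > 50 | > 30 |
| -5 | > 45 | > 25 |
| -2 | > 42 | > 22 |
| +2 | > 38 | > 18 |
| +5 | > 35 | > 15 |
| +10 | > 30 | > 10 |

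**5. Where the change limits matter.** The change limit is reached before the absolute limit only if baseline systolic is below 180 - 40 = 140 mmHg, or baseline diastolic is below 100 - 20 = 80 mmHg. Above those values the absolute limit acts first. Entry permits up to 160/90 mmHg.

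**6. Persistence.** Three readings at the minimum spacing span 2 x 2 = 4 minutes, so a scheduled set at that spacing cannot by itself show 10-minute persistence. Extra readings are needed in either posture.

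**7. SAP tables.** SAP 4.6.5.1 counts rises of more than 40 and more than 20 mmHg. It says: "Systolic and diastolic blood pressure will be measured in triplicates and the mean of the three measurements will be collected in the EDC". Those recorded values are the scheduled seated ones at both baseline and follow-up, so the tables are consistent in posture.

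**The case against.** The strongest reply is that supine is loose wording and that sites will apply the limits to seated values, as the SAP tables in effect do. The Amendment 2 summary supports this: it explains the tighter diastolic entry limit by the distance to the stopping criteria, which sets a sitting limit directly against the supine one. That is fair evidence of intent. It does not change the wording of a mandatory rule, and it favours the seated rewording.

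A reader might infer that the rule cannot be applied at all and that every site must improvise. The documents do not go that far. A baseline definition exists, even if it is written for analysis. Participants already lie down before the Day 1 ECG, so a supine pressure could be taken then, although nothing requires it. Confirmatory readings are needed anyway.

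A reader might also infer that participants will be wrongly stopped or wrongly continued. That is not shown. Two of the three ways of applying the rule give no offset, d is not in the documents, and nothing indicates how many sites would mix postures. Section 7.1 also lets the investigator or sponsor stop dosing for safety. This discretion limits the harm, but it does not settle which baseline the mandatory limits use.

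Nor should the point be tied to the animal signal in Protocol Table 2. That was a transient rise 0.5 to 8 hours after dosing, and 8.2.2 places vital signs before dosing, so scheduled readings would largely miss it in either posture.

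**Conclusion.** The rule is wrong as written, and the severity is minor. Two of the four hypertension limits refer to a supine baseline that the protocol does not schedule. Taken literally with the defined baseline, they become 40 - d and 20 - d mmHg, with d unknown. The inconsistency itself is certain from the text; its practical effect is not quantified. The illustrative range rests wholly on assumed values of d, constant within a participant.

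It would be a mistake to read this as a flaw in the absolute limits, the SAP vital-sign tables or the primary analysis. The absolute limits need no baseline and the tables use seated values throughout. The primary analysis is of LDL-C, and SAP Table 3 specifies how permanent discontinuation is handled whatever its cause.

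**What to change.** Reword the hypertension bullet in Protocol 7.1.2 to seated pressure measured as in 8.2.2, compared with the seated pre-dose baseline. Keep the limits and the 10-minute persistence requirement, confirmed by repeat seated readings at least 10 minutes later. The cost is one bullet in a short amendment, with no new scheduled measurement. It would probably be classed as substantial, because Amendment 2 classed its clarification of the respiratory stopping criteria that way.

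If the sponsor prefers supine for clinical reasons, add supine pressure by the 8.2.2 method (mean of three readings at least 2 minutes apart) at Day 1 pre-dose and at each later on-treatment visit: Days 8, 15, 29 and 57. That is 5 visits x 3 = 15 extra readings per participant, with matching eCRF fields, and a line in SAP 4.6.5.1 saying which readings its tables use. Day 85 can be left out because dosing ends on Day 84. Within the 3-day window, only a visit on Days 82 to 84 could precede a remaining dose, with at most 3 dosing days left.
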